The main study will be conducted in 3 phases: a maximum 6-week screening phase, a 52-week double-blind intervention phase, and a safety follow-up phase with a post-intervention follow-up visit at 12 weeks after the participant's last dose of study intervention to collect any AEs since the last study visit.

Participants who complete the main study (Week 0 through 52: ie, after the Week 48 evaluation, prior to Week 52 evaluation) and who, in the opinion of the investigator, may benefit from continued treatment, will participate in the LTE by signing the ICF before or at Week 52. The duration of individual participation will be approximately 66 weeks without LTE and 118 weeks with LTE.

Two planned database locks (DBLs) will occur: EOS of the main study (Week 52 visit for participants who entered LTE or safety follow up visit for participants who did not enter LTE, hereinafter referred to as "Week 52 DBL"), and EOS of LTE (Week 112 visit, hereinafter referred to as "Final DBL").

Key efficacy assessments will include mRSS, ACR CRISS score; pulmonary function tests: FVC and % of predicted FVC, and DLCO (ml/min/mm Hg) and % of predicted DLCO (hemoglobin-corrected); PhGA; and PGA. Key safety assessments include the monitoring of AEs (including SAEs, AEs of special interest [AESIs], infections, injection-site reactions, adverse events temporally associated with infusion, and hypersensitivity reactions), physical examinations, vital sign measurements, electrocardiogram (ECG) measurements, clinical laboratory tests, ILD (assessed by centrally read HRCT), and tuberculosis (TB) evaluations. Additionally, PK, biomarker, and immunogenicity assessments will also be performed in this study

NUMBER OF PARTICIPANTS

The study will target to enroll a total of approximately 56 participants with 28 participants planned per intervention group.

INTERVENTION GROUPS AND DURATION

Participants will be randomly assigned in a 1:1 ratio to 1 of the following study intervention groups:

- Guselkumab (Group/Arm A): Guselkumab 400 mg IV administration Weeks 0, 4, and 8 (induction) followed by guselkumab 200 mg SC administration Q4W from Week 12 until Week 48 (maintenance)
- Placebo (Group/Arm B): Matching placebo IV administration Weeks 0, 4, and 8 (induction) followed by matching placebo SC administration Q4W from Week 12 until Week 48 (maintenance)

During the LTE, all participants will receive guselkumab treatment in LTE as below depending on the arms they were in the main study:

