4.1.1. Long-term Extension

The objective of LTE is to evaluate the long-term safety and efficacy of guselkumab in SSc patients. The LTE begins with the completion of the assessments at the Week 52, and LTE continues through LTE Week 104. The LTE includes a safety follow-up phase with a post-intervention follow-up visit at LTE Week 112 (12 weeks after the participant's last dose of study intervention).

Participants who complete the main study and who, in the opinion of the investigator, may benefit from continued treatment, will participate in the LTE by signing the ICF before or at Week 52, will receive guselkumab treatment in LTE as below depending on the arms they were in the main study (Week 0 through 52).

- Group/Arm A (guselkumab arm from the main study): Guselkumab 200 mg SC and placebo IV at LTE Weeks 52, 56, and 60 followed by guselkumab 200 mg SC Q4W from LTE Week 64 until Week 100.
- Group/Arm B (placebo arm from the main study): Placebo SC and guselkumab 400 mg IV at LTE Weeks 52, 56, and 60 followed by guselkumab 200 mg SC Q4W from LTE Week 64 until Week 100.

During the LTE, all protocol-allowed concomitant medications and rescue medications may be administered at the discretion of the investigator. Prohibited medications listed in Section 6.1 continue to be prohibited in the LTE.

All study evaluations to be performed during the LTE are listed in the Section 1.3 Schedule of Activities (SoA).

The study blind will be maintained until the Week 52 DBL and participants will continue to receive study intervention in a blinded manner at all visits until that time.

The final DBL will occur when all participants complete the LTE (EOS for LTE period).

At selected visits during the LTE, at the discretion of the investigator and participant, and after appropriate and documented training, participants will self-administer study intervention. Details are provided in Section 4.1.2 Self-Administration of Study Intervention.

A diagram of the study design is provided in Section 1.2. Schema.

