5.1.3. Intervention Group

The population will be the FAS defined in Section 4 for all the efficacy analysis, and the assigned treatment group for each participant will be used regardless of the actual treatment received.

All the safety analyses will be performed on safety analysis set, and by the actual treatment participants received regardless of the assigned treatment.

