5.7. Safety Analyses

All safety analyses will be based on the safety analysis set and presented by actual intervention received, unless otherwise specified.

For all continuous safety variables, descriptive statistics by intervention group will include the N, mean, standard deviation, median, minimum, and maximum. Categorical variables will be summarized by intervention group using frequency counts and percentages.

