5.7.2. Adverse Events

The verbatim terms used in the CRF by investigators to identify adverse events will be coded using the Medical Dictionary for Regulatory Activities (MedDRA). Any AE occurring at or after the initial administration of study intervention is considered to be treatment emergent. If the event occurs on the day of the initial administration of study intervention, and either event time or time of administration are missing, then the event will be assumed to be treatment emergent. If the event date is recorded as partial or completely missing, then the event will be considered to be treatment emergent unless it is known to be prior to the first administration of study intervention based on partial onset date or resolution date. All reported treatment-emergent adverse events will be included in the analysis. For each adverse event, the number and percentage of participants who experience at least 1 occurrence of the given event will be summarized by intervention group.

Summary tables will be provided for treatment-emergent adverse events in the main study period and LTE period:

- AEs
- Serious AEs (SAEs)
- AEs leading to discontinuation of study intervention
- AEs by severity
- AEs by relationship to study intervention
- AEs leading to drug interruption

- Infusion reaction
- Injection site reaction
- Covid-19 related AEs and SAEs

In addition to the summary tables, listings will be provided for participants who:

- Had SAEs
- Had AEs leading to discontinuation of study intervention

Incidence of other treatment-emergent adverse events of special interest will be summarized. See [Appendix 8](#) for list of adverse events in each category.

Deaths will be displayed by actual intervention received. Frequencies for the following parameters will be included in the summary table:

- Number of participants who died
- Cause of death
- Relationship to study intervention (yes/no)

A listing of participants who died will be provided.

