5.8.2. Immunogenicity

Immunogenicity analyses will be performed on the Immunogenicity analysis set (Section 4). The anti-guselkumab antibodies summary and analysis will be based on the observed data; therefore, no imputation of missing data will be performed.

The incidence of positive antibodies, neutralizing antibody (Nabs, as appropriate) and the maximum titers of antibodies to guselkumab from Week 0 to Week 24/52/104 will be summarized by the intervention group.

The summary of following endpoints at the following visit will be presented by the intervention group and Subject ADA status who have at least one positive ADA sample or no positive ADA sample evaluated at the same visit:

- Change from baseline in mRSS at Week 24/52
- ACR CRISS responder (participants who achieve a score ACR CRISS \geq 0.6) at Week 24/52
- Injection-Site Reactions status through Week 52/104

If appropriate, these summary by category of titer level for positive participants will also be considered.

A listing of individual immune response including antibody status (negative/positive) for both sample level and participant level, Nab status, serum maximum titers, serum guselkumab concentration, Injection-Site Reactions status and change from baseline in mRSS at all sampling time points for all participants will be provided. In addition, self-study intervention administration status will also be included in the listing.

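### The LTE reaction tables take no account of the product given by each route: Arm A's placebo infusions fall under a guselkumab group, and 3 of Arm B's 13 SC visits are placebo mixed with active

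*SAP*

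**What the plan says.** **LTE regimen.** Protocol 4.1.1 gives Arm A "Guselkumab 200 mg SC and placebo IV at LTE Weeks 52, 56, and 60 followed by guselkumab 200 mg SC Q4W" and Arm B "Placebo SC and guselkumab 400 mg IV at LTE Weeks 52, 56, and 60 followed by guselkumab 200 mg SC Q4W", in both cases "from LTE Week 64 until Week 100". The Protocol synopsis adds that "all participants will receive guselkumab treatment in LTE as below depending on the arms they were in the main study", so the LTE has no placebo group.

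**Reaction tables.** SAP 5.7.2: "Summary tables will be provided for treatment-emergent adverse events in the main study period and LTE period". Infusion reaction and injection site reaction are both on the list that follows. Each event is summarised as the number and percentage of participants with one or more occurrences, by intervention group.

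**Grouping rule.** SAP 5.7: "All safety analyses will be based on the safety analysis set and presented by actual intervention received, unless otherwise specified". SAP 5.1.3 sets this at participant level: "by the actual treatment participants received regardless of the assigned treatment". SAP Table 3 defines a safety set for the LTE but gives it no grouping note.

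**What counts as a reaction.** The Protocol Introduction defines study intervention as guselkumab and placebo. Protocol 8.2.7 counts any adverse reaction at an SC study intervention site. Protocol 8.2.6 covers any non-laboratory AE during, or up to an hour after, an IV infusion of study intervention. A reaction to placebo product therefore meets both definitions.

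**Antibody cross-table.** SAP 5.8.2 summarises "Injection-Site Reactions status through Week 52/104" by intervention group and anti-guselkumab antibody status.

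**The concern.** In the main study each visit has one route and one product, so a participant's group identifies what was infused or injected. That stops being true at LTE Weeks 52, 56 and 60, when every participant receives one active and one placebo product by different routes. A participant-level grouping rule cannot express this, and nothing in SAP 5.1.3, 5.7, 5.7.2, Table 3 or the appendices ties a reaction to the product given by that route at that visit. The exposure summary in SAP 5.7.1 counts administrations without splitting by product or route, so it gives no matching denominator.

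At stake is what the tables will be taken to show. Arm A's infusion reactions appear under guselkumab in both periods, although the infused product changes from active to placebo. A reader could take a lower LTE figure for better tolerability. Arm B's injection-site table combines placebo-site and active-site reactions, and participant-level counts cannot be separated afterwards. In the antibody cross-table, reactions at placebo sites say nothing about whether antibodies go with reactions to guselkumab injections.

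**Working it through.** The plan states no reaction count or rate, so there is no figure of its own to reproduce. The check is a count of scheduled administrations from Protocol 4.1.1 and 6.1 (SAP 1.2 repeats the regimens).

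**Visits**
- Main-study infusions: Weeks 0, 4, 8 = 3.
- Main-study SC visits: Weeks 12 to 48 every 4 weeks, (48 − 12)/4 + 1 = 10.
- LTE infusions: Weeks 52, 56, 60 = 3.
- LTE SC visits: Weeks 52 to 100 every 4 weeks, (100 − 52)/4 + 1 = 13.
- LTE SC visits active in both arms: Weeks 64 to 100, (100 − 64)/4 + 1 = 10.

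**Active administrations**

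| | Main IV | LTE IV | Main SC | LTE SC |
|---|---|---|---|---|
| Arm A | 3 of 3 | 0 of 3 | 10 of 10 | 13 of 13 |
| Arm B | 0 of 3 | 3 of 3 | 0 of 10 | 10 of 13 |

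- Arm B, LTE SC placebo share: 3/13 = 23.1%.
- Arm B, SC placebo share from Week 0 through Week 104: (10 + 3)/(10 + 13) = 13/23 = 56.5%. The bullet in SAP 5.8.2 gives no start point. The antibody-incidence sentence earlier in that section runs from Week 0, which is the reading used here. Counted from Week 52 the share is again 3/13.

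**Two possible column layouts.** The SAP does not write out column labels for the LTE safety tables.
- By main-study arm: Arm A's placebo-infusion reactions sit under guselkumab. Arm B's infusion column is purely active. Arm B's injection-site column mixes 3 placebo and 10 active visits.
- Pooled as guselkumab: with equal entry from both arms, 3/6 = 50% of LTE infusions and 3/26 = 11.5% of LTE SC visits are placebo.

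**Illustration of the Arm B mixing.** Assume a reaction probability p per SC visit, the same for both products and independent between visits. The share of participants with at least one reaction is 1 − (1 − p)^13 over all LTE visits and 1 − (1 − p)^10 over active visits only.

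| Assumed p | All 13 visits | 10 active visits |
|---|---|---|
| 0.5% | 6.3% | 4.9% |
| 1% | 12.2% | 9.6% |
| 2% | 23.1% | 18.3% |
| 5% | 48.7% | 40.1% |

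If all 28 planned Arm B participants entered the LTE, p = 2% would give 6.47 expected participants against 5.12. These values of p are assumptions and do not come from the documents.

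**The case against.** The strongest reply is that the SAP tabulates by intervention group and names no overall column in 5.7.2, although it asks for one explicitly in 5.2 and Appendix 3. SAP 5.8.1 presents Weeks 52 to 104 by intervention group and, for self-administration, by the arm held in the double-blind period. On that reading the LTE infusion table already has one column of placebo infusions and one of active infusions, and a footnote would do. This largely stands for infusions. A reader might infer that the guselkumab infusion-reaction rate is roughly halved. That would need pooled arms, equal entry and rare placebo reactions, and the SAP does not plan the pooling. The layout does not help Arm B's injection-site table, where both products share a column.

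Three other tempting readings also go too far:
- **Self-injection safety is contaminated.** Placebo SC ends at Week 60. Self-administration may begin from Week 68 (Protocol Table 2, note c) and at-home dosing from Week 84 (Protocol 4.1.2), so all those doses are active.
- **An Arm A infusion event is purely a placebo event.** Protocol 8.2.6 defines these events by timing, and Arm A receives active SC guselkumab at the same visits. A systemic event there may be drug-related, although it is not a reaction to a guselkumab infusion.
- **A planned main-versus-LTE comparison is biased.** The SAP specifies no such contrast. The risk lies in how two tables are read side by side.

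SAP 5.8.2 also requires a participant listing of reaction status and antibody status at all sampling times. That lets a determined reader look behind the cross-table, but it does not correct the table.

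**Conclusion.** The point holds for the LTE. Under the stated participant-level rule, 3 of 3 Arm A LTE infusions are placebo yet reported under a guselkumab-treated group, and 3 of 13 Arm B LTE SC visits (23%) are placebo and inseparable from 10 active ones. The antibody cross-table through Week 104 can draw on 13 of 23 (57%) placebo SC visits in Arm B if it counts from Week 0. These are shares of scheduled administrations, assuming full attendance. They are not shares of reactions, and no count of misattributed reactions can be given. Main-study tables are sound. No hypothesis test or decision rule is touched. It is still worth correcting, because following the SAP as written puts placebo-product reactions under the wrong description.

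**What to change.** - **SAP 5.7.2.** Present LTE infusion and injection-site reactions by main-study arm, route and product given at the associated visit. For Arm B SC, separate Weeks 52 to 60 (placebo) from Weeks 64 to 100 (active). Use the matching number of participants or administrations as denominator. State how a reaction between visits is linked to an administration, for example to the most recent one by that route.
- **Footnote.** Say that Arm A also received active SC guselkumab at its placebo-infusion visits, so systemic events there may still be drug-related.
- **SAP 5.8.2.** Count only reactions at guselkumab injections when crossing injection-site reaction status with antibody status, and state the start of the counting period.

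The cost is SAP wording, a little programming and sparser cells. No new data are needed: Protocol 6.4 has the details of each administration recorded, and Protocol 6.3 has the study intervention number entered in the eCRF. Protocol 9.4 has the SAP finalised before each database lock, so the change can be made before the Final DBL.

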	Crohn's disease program in a participant who received guselkumab 1200 mg intravenous (IV) at Weeks 0, 4, and 8, and 200 mg subcutaneous (SC) at Week 12. Based on the hepatocellular pattern of injury, temporal relationship of the event to guselkumab exposure, and the exclusion of alternative etiologies, this event may represent druginduced liver injury possibly related to guselkumab. Alanine aminotransferase (ALT)/ aspartate aminotransferase AST abnormailities are a known risk for guselkumab, and that in the psoriatic arthritis studies, patients receiving guselkumab every 4 weeks (Q4W) were more likely to experience transaminase elevations than those receiving it every 8 weeks (Q8W).	accordance with regulatory guidance (FDA 2009). In addition, the induction doses evaluated in this clinical program will not exceed 400 mg IV. • Participants with marked liver enzyme elevations or symptoms or signs of liver dysfunction (eg, jaundice), should undergo a thorough investigation for possible causes of liver injury. A participant must have their study intervention discontinued if the participant has severe liver test abnormalities that are not transient and are not explained by other etiologies (Section 7.1 and Section 10.6).
Immunosuppression	It is unknown if guselkumab in combination with other immunosuppressives increases the risk of diseases associated with immunosuppression, such as infections or malignancy.	• In order to minimize the theoretical increased risk of infection or malignancy with the combination of guselkumab with immunosuppressive therapy, the baseline dose of oral corticosteroids on study entry is limited ≤10 mg of prednisolone or equivalent per day which must be at a stable dose ≥4 weeks prior to first dose of study intervention. Furthermore, participants receiving investigational or approved immunomodulatory agents like IL-23 inhibitor therapy, IL-12/23 inhibitors, or IL-17 inhibitors, failed for efficacy in SSc or within 12 weeks or 5 half-lives

CONFIDENTIAL – FOIA Exemptions Apply in U.S.

27

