3. OBJECTIVES AND ENDPOINTS

	Objectives		Endpoints
Pri	mary		
•	To evaluate the efficacy of guselkumab in participants with systemic sclerosis (SSc)	•	Change from baseline in Modified Rodnan Skin Score (mRSS) at Week 24
Sec	ondary		
•	To evaluate the additional efficacy of guselkumab in participants with SSc	•	Change from baseline in mRSS at Week 52
		•	The proportion of participants who experience worsening of mRSS at Week 24 and Week 52
		•	The proportion of participants achieving a score of 0.6 in American College of Rheumatology Combined Response Index in dcSSc (ACR CRISS) at Week 24 and Week 52
		•	Change from baseline in forced vital capacity (FVC) and percent predicted FVC at Week 24 and Week 52
		•	Change from baseline in the measured absolute diffusing capacity of the lung for carbon monoxide (DLCO) and the derived percent predicted DLCO at Week 24 and Week 52
		•	Change from baseline in digital ulcer counts at Week 24 and Week 52
		•	Change from baseline in Health Assessment Questionnaire-Disability Index (HAQ-DI) score at Week 24 and Week 52
•	To evaluate the safety and tolerability of guselkumab in participants with SSc	•	Number and proportion of participants with treatment-emergent adverse events (AEs) and serious adverse events (SAEs) or adverse events of special interest (AESI) from baseline through Week 24, Week 52, Week 76 and Week 104
•	To evaluate the pharmacokinetic (PK) and	•	Serum guselkumab concentrations
	immunogenicity of guselkumab	•	Incidence of anti-guselkumab antibody
Ex	oloratory		
•	To evaluate the other efficacy of guselkumab in participants with SSc	•	Time to disease worsening: Increase from baseline ≥5 and ≥20% in mRSS OR decrease >10% from baseline in FVC %
		•	The proportion of participants who experience FVC decline compared with baseline at Week 24 and Week 52
		•	The proportion of participants who experience worsening of FVC at Week 24 and Week 52
		•	Change from baseline in fibrotic change assessed with high-resolution computed tomography (HRCT) at Week 24 and Week 52 in participants

CONFIDENTIAL – FOIA Exemptions Apply in U.S.

29

Objectives		Endpoints
		with baseline fibrosis/fibrotic changes
	•	The proportion of participants who experience worsening of fibrotic change assessed with HRCT at Week 24 and Week 52
	•	Change from baseline in Frequency Scale for the Symptoms of Gastroesophageal reflux disease (FSSG) score at Week 24 and Week 52
	•	Assessment of nailfold capillaries at Week 24 and Week 52

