Participants may be treated with following medications for pulmonary arterial hypertension: endothelin receptor antagonists (eg, bosentan, ambrisentan and macitentan), phosphodiesterase 5 inhibitors (eg, sildenafil and tadalafil), and prostacyclins (eg, epoprostenol, iloprost and treprostinil). The dose should remain stable during the study.

ACE Inhibitors, Calcium-Channel Blockers, or Protein-Pump Inhibitors

Participants receiving ACE inhibitors, calcium-channel blockers, proton-pump inhibitors, and/or oral vasodilators have to be on a stable dose during the study, unless dose adjustments are required for safety reasons.

Prohibited and restricted therapies

During the study

IL-23 inhibitor therapy (including but not limited to guselkumab, risankizumab, tildrakizumab, brazikumab, mirikizumab)

tocilizumab

sirukumab, sarilumab, mavrilimumab, abatacept, belimumab

IL-12/23 inhibitors (ustekinumab)

IL-17 inhibitors (secukinumab, ixekizumab, brodalumab)

tyrosine kinase inhibitor (nintedanib)

Any live viral or live bacterial vaccination

Rituximab

Any cytotoxic agents (cyclophosphamide, chlorambucil, nitrogen mustard, or other alkylating agents)

Intravenous immunoglobulin (IVIG), apheresis therapy (plasmapheresis or leukopheresis)

Systemic immunosuppressive agents (including but not limited to cyclosporine A, azathioprine, tacrolimus, sirolimus, methotrexate, sulfasalazine, leflunomide with cholestyramine washout or mycophenolate mofetil/mycophenolic acid)

Intramuscular, intra-articular, intrabursal, epidural, intra-lesional or IV GCs

Pirfenidone

Systemic and topical Janus kinase inhibitors (eg, tofacitinib, upadacitinib)

Other biologics

Any investigational agents/treatments

The sponsor must be notified in advance (or as soon as possible thereafter) of any instances in which prohibited therapies are administered.

Rescue Medication

In the event that a participant experiences worsening criteria (Criteria: increase from baseline ≥5 in mRSS), investigators will have the option to treat with protocol-allowed rescue therapy after Week 24.

Oral Corticosteroid ≤20 mg/day of prednisolone or equivalent

Immunomodulator (Azathioprine), within the approved dose for SSc

If rescue therapy as stipulated above fails to control SSc symptoms sufficiently, the investigator should consider discontinuing the patient from the study.

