1.1. Objectives and Endpoints

Objectives and endpoints of this study are listed in [Table 1](#).

Table 1: Objectives and Endpoints

Objectives	Endpoints
Primary	

 To evaluate the efficacy of guselkumab in participants with SSc 	
 Change from baseline in Modified Rodnan Skin Score (mRSS) at Week 24
Secondary	

 To evaluate the additional efficacy of guselkumab in participants with SSc 	
 Change from baseline in mRSS at Week 52 The proportion of participants who experience worsening of mRSS at Week 24 and Week 52 The proportion of participants achieving a score of 0.6 in American College of Rheumatology Combined Response Index in dcSSc (ACR CRISS) at Week 24 and Week 52 Change from baseline in forced vital capacity (FVC) and percent predicted FVC at Week 24 and Week 52 Change from baseline in the measured absolute diffusing capacity of the lung for carbon monoxide (DLCO) and the derived percent predicted DLCO at Week 24 and Week 52 Change from baseline in digital ulcer counts at Week 24 and Week 52 Change from baseline in Health Assessment Questionnaire-Disability Index (HAQ-DI) score at Week 24 and Week 52

 To evaluate the safety and tolerability of guselkumab in participants with SSc 	
 Number and proportion of participants with treatment-emergent adverse events (AEs) and serious adverse events (SAEs) or adverse events of special interest (AESI)

Objectives	Endpoints
	through Week 24, Week 52, Week 76 and Week 104

 • To evaluate the pharmacokinetic(s) and immunogenicity of guselkumab 	
 • Serum guselkumab concentrations • Incidence of anti-guselkumab antibody
Exploratory	

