5.7.3. Additional Safety Assessments

5.7.3.1. Clinical Laboratory Tests

Clinical laboratory tests will be displayed for the participants included in the safety analysis set.

Descriptive statistics will be presented for selected chemistry, hematology, and urinalysis (pH and specific gravity) laboratory tests at scheduled time points.

Change from baseline over time through Week 52 will be summarized for selected chemistry, hematology, and urinalysis (pH, and specific gravity) tests and displayed by intervention group. A box plot of change from baseline over time through Week 52 will be provided for the following laboratory tests: hematology: hemoglobin, platelets, total WBC, absolute lymphocytes, and absolute neutrophils; chemistry: ALT, AST, Alkaline phosphatase and total bilirubin.

Applicable lab results are to be graded based on National Cancer Institute Common Terminology Criteria for Adverse Events (NCI-CTCAE) version 5.0. The laboratory tests not included in the NCI-CTCAE criteria will not be presented in the corresponding tables or listings.

Summary of maximum postbaseline NCI-CTCAE toxicity grade through Week 52 will be presented. Additionally, shift table from baseline laboratory value to the worst toxicity grade through Week 52 in chemistry and hematology tests with NCI-CTCAE will be summarized for the following lab parameters: hematology: hemoglobin, platelets, total WBC, absolute lymphocytes, and absolute neutrophils; chemistry: ALT, AST, Alkaline phosphatase and total bilirubin.

Proportion of participants with maximum postbaseline ALT and AST through Week 52 will be provided for the categories:

- >1 to ≤ 3 x ULN
- >3 to ≤ 5 x ULN
- >5 to ≤ 10 x ULN
- >10 to ≤ 20 x ULN
- >20 x ULN

Besides, proportion of participants with total bilirubin >2 x ULN and either AST or ALT ≥ 3 x ULN at the same timepoint will also be provided.

In addition, proportion of participants with maximum postbaseline alkaline phosphatase through Week 52 will be provided for the categories:

- ≤ 1 x ULN
- >1 to ≤ 1.5 x ULN
- >1.5 to ≤ 2.5 x ULN
- >2.5 to ≤ 5 x ULN
- >5 to ≤ 20 x ULN
- >20 x ULN

Above analysis will also be summarized through LTE period.

Listings of participants with any abnormal postbaseline laboratory values of NCI-CTCAE grade ≥ 2 or any abnormal postbaseline laboratory values of reference range will also be provided.

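### The SAP's adverse event tables cover only the main and LTE periods, so they omit the Week 24 and Week 76 cuts of the secondary safety endpoint; the Week 24 cut matters most because rescue opens after it

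*SAP*

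**What the plan says.** The safety endpoint sits under the secondary objectives in both documents. SAP 1.1, Table 1, sets its time points as "through Week 24, Week 52, Week 76 and Week 104". Protocol Section 3 has the same four and counts from baseline: "interest (AESI) from baseline through Week 24, Week 52, Week 76 and Week 104".

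The list of tables to be programmed is in SAP 5.7.2, which states: "Summary tables will be provided for treatment-emergent adverse events in the main study period and LTE period". The AESI sentence gives no period: "Incidence of other treatment-emergent adverse events of special interest will be summarized". The treatment-emergent window opens at first dose and has no stated end: "Any AE occurring at or after the initial administration of study intervention is considered to be treatment emergent".

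On rescue, protocol 6.8 says that if mRSS has risen by at least 5 from baseline, "investigators will have the option to treat with protocol-allowed rescue therapy after Week 24". The agents are oral corticosteroid up to 20 mg/day (the background limit is 10 mg/day) and azathioprine. The risk table in protocol 2.3.1 states: "It is unknown if guselkumab in combination with other immunosuppressives increases the risk of diseases associated with immunosuppression, such as infections or malignancy".

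**The concern.** An endpoint listed in both documents has no matching output in the section that specifies the outputs, and SAP Appendix 2 records no departure from the protocol. A programmer working from 5.7.2 would produce two period tables and no count through Week 24 or Week 76.

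Week 24 is the costly omission. It is the last randomised safety comparison before protocol-allowed rescue opens. After it, some participants in either arm may be taking more immunosuppression, and the protocol itself calls the combination with guselkumab an unknown risk. The SAP handles rescue explicitly as an intercurrent event for Week 52 efficacy (5.4.2.2) and as an event in time to disease worsening (5.5.2). In safety it reports rescue use by visit and in listings (Appendix 5), without linking it to adverse events.

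If guselkumab works, rescue should be more common on placebo. Infections arising on rescue would then raise the placebo count and shrink any excess on guselkumab in the main-period table. Protocol 4.1 names infections among the key safety assessments. The SAP specifies only opportunistic infections, active TB and COVID-19 as infection categories.

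**Working it through.** **Step 1: endpoint cuts against planned tables.**

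| Endpoint cut (SAP Table 1, protocol Section 3) | Adverse event table in SAP 5.7 |
|---|---|
| Through Week 24 | None |
| Through Week 52 | Main-period table, approximately: the main study ends at Week 52 for LTE entrants but at the Week 60 follow-up for others |
| Through Week 76 | None |
| Through Week 104 | An LTE-period table; not stated to be cumulative from baseline |

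Participant counts from the main and LTE tables cannot be added to give a cumulative count, because a participant with events in both periods would be counted twice. The SAP does carry interim cuts elsewhere: 5.6 gives efficacy through Weeks 24, 52, 76 and 104, and 5.8.2 gives antibody incidence to Weeks 24, 52 and 104. The gap is specific to adverse events.

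**Step 2: share of the main period after rescue opens.** (52 − 24)/52 = 28/52 = 53.8%. For a participant followed to Week 60, (60 − 24)/60 = 60%.

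**Step 3: illustrative size.** The plan has no figure of its own to reproduce here, and the documents give no infection or rescue rates. Every rate below is an assumption:

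- placebo infection risk by Week 52 without rescue, p = 30%, 40% or 50%
- true hazard ratio for guselkumab, h = 1.5
- rescue multiplies the infection hazard by k = 1.5 or 2
- a fraction r of the arm is rescued, all exactly at Week 24

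Weekly hazard: λ = −ln(1 − p)/52.

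Risk by Week 52: R(h, r) = 1 − exp(−24λh) × [(1 − r) exp(−28λh) + r exp(−28λhk)], with h = 1 for placebo.

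Worked case, p = 50%, k = 2: λ = 0.6931/52 = 0.01333.

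- No rescue: guselkumab 0.646, placebo 0.500, ratio 1.29.
- Rescue in 40% of placebo and 10% of guselkumab: guselkumab 0.662, placebo 0.562, ratio 1.18.

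| Rescued, placebo / guselkumab | Week 52 risk ratio, range over p and k |
|---|---|
| None | 1.29-1.38 |
| 20% / 10% | 1.25-1.35 |
| 40% / 20% | 1.20-1.32 |
| 40% / 10% | 1.18-1.30 |
| 30% / 30% | 1.27-1.37 |

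The Week 24 ratio is 1.39-1.44. It exceeds the no-rescue Week 52 ratio only because risk ratios move towards 1 as cumulative risk rises. The effect of rescue is therefore read within the Week 52 column. With no true effect (h = 1), the 20%/10% and 40%/20% cases give ratios of 0.93-0.98.

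In participants, the extra placebo infections among 28 run from 28 × (0.313 − 0.300) = 0.4 (p = 30%, 20% rescued, k = 1.5) to 28 × (0.562 − 0.500) = 1.7 (p = 50%, 40% rescued, k = 2).

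**The case against.** The strongest reply is that this is a wording gap. The endpoint is still in SAP Table 1, 5.7.2 does not forbid a Week 24 table, and the AESI sentence names no period, so nothing overrides Table 1 there. Counting all treatment-emergent events regardless of rescue is a legitimate safety convention, and safety need not copy the efficacy intercurrent-event rules. All of that is fair. It does not remove the mismatch: 5.7.2 is where the tables are specified, and it specifies two periods.

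Several stronger readings are tempting, and the documents do not support them:

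- **Rescue would hide an infection signal.** With 28 per arm, descriptive safety and no stated rates, the illustration supports modest dilution only. It also assumes that everyone rescued starts at Week 24, the earliest possible time, so it leans towards overstating the effect.
- **The Week 24 comparison is rescue-free.** Protocol 6.8 allows up to 20 mg/day of steroid for 2 weeks for non-SSc conditions at any time, and SAP Appendix 11 provides for rescue given before Week 24. Week 24 is before rescue is allowed, which is not the same as free of added steroid.
- **Laboratory maxima stop at Week 52.** The sentence "Proportion of participants with maximum postbaseline ALT and AST through Week 52 will be provided for the categories" could suggest this, but 5.7.3.1 goes on to extend those summaries through the LTE.
- **The endpoint already requires infection or ALT/AST tables at Week 24.** It names TEAEs, SAEs and AESIs only. An infection row is a recommended addition.
- **Safety ignores rescue entirely.** Rescue use is summarised by visit and listed, and SAEs are listed, so individual cases can be traced.

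A before/after-rescue split has its own weakness. It conditions on a post-randomisation event driven by worsening, with unequal exposure either side, so it can only be descriptive.

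**Conclusion.** The mismatch is confirmed from the text and rests on no assumption. SAP 5.7.2 does not deliver the Week 24 and Week 76 cuts of the secondary safety endpoint, delivers the Week 52 cut only approximately, does not state a cumulative Week 104 count, and Appendix 2 declares no change.

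The consequence for reading infection risk is real but modest, and its size is unknown. For a true hazard ratio of 1.5, unequal rescue moves the Week 52 risk ratio from 1.29-1.38 to about 1.18-1.35. That depends on assumed infection risks, rescue fractions and multipliers, and on placebo being rescued more often. If rescue is balanced the ratio barely moves (1.27-1.37), and if rescue is rare the effect is small. The case for the change rests on delivering the stated endpoint. The rescue argument explains why Week 24 is the cut least worth losing.

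**What to change.** In SAP 5.7.2, specify the TEAE, SAE and AESI tables by arm, cumulatively from baseline through Weeks 24, 52, 76 and 104, as Table 1 states. Add an infections row and a serious-infections row at the same cuts. Label the Week 76 and Week 104 columns by treatment sequence, since all LTE participants receive guselkumab and those columns are no longer a placebo comparison. The existing main-period and LTE tables can stay.

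Optionally, for events after Week 24, flag whether onset came before or after the first rescue dose, with person-time for each, and draw no causal comparison. Before defining that flag, reconcile the places in protocol 6.8 and SAP Appendix 11 where azathioprine appears both among the therapies prohibited during the study and as rescue.

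The cost is SAP wording and a few more tables from adverse event dates and rescue records already collected. Counts will be small, so the tables are descriptive.
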